Protocol ID: U20-11-4312 ([name]) Protocol Title: Effects of Healing Touch on Pain and Anxiety in Women After Cesarean Delivery NCT: 05053360 Date: 11/22/2022

Inova Health System IHS Principal Investigator: [name], MSN, RNC-OB, NPD-BC, C-EFM

ABSTRACT

Title: Effects of Healing Touch on Pain and Anxiety in Women After Cesarean Delivery

Short Title: Healing Touch After Cesarean

Rationale: Pain and anxiety are the most common complications after cesarean birth. Pain and anxiety can impair the mother's ability to optimally care for herself and her newborn. It is important for health care providers to evaluate options post-operatively to maximize symptom management and quality of care for these patients, including the option of complementary therapies such as Healing Touch (HT).

Objectives: Primary outcomes will include the differences between the intervention and control groups' pre-/postintervention levels of pain (Numeric Rating Scale) and anxiety (Numeric Rating scale). Secondary outcomes include the relationship between HT and demographic information of the subjects. As well, the feasibility of introducing HT as a therapy for postpartum women will be assessed.

Study Type: Randomized Control Trial

Study Design: The total sample size for the proposed study will include 160 participants. The study will include patients' age \geq 18 years having a scheduled cesarean delivery at Inova Loudoun Hospital (ILH), Inova Fair Oaks Hospital (IFOH), Inova Alexandria Hospital (IAH), and Inova Fairfax Medical Campus (IFMC) who will be enrolled prior to their scheduled cesarean delivery. Inclusion criteria for the HT group are (1) the ability to ensure informed consent and completion of study assessments; (2) the ability to speak, read, and understand English; (3) scheduled cesarean delivery; (4) \geq 18 years of age. Exclusion criteria for the HT group are (1) Non-English speaking due to the fidelity and variability of the research (2) Prisoners, (3) Isolation precautions, (4) active psychosis and impaired cognition, and (5) cesarean delivery who delivers prior to scheduled cesarean date. The study is expected to last about one year from study initiation through analysis.

Study Methodology: One to two weeks prior to a scheduled cesarean delivery, a member of the research team will call and screen women for eligibility on the study. If the woman electronically completes the consent form, they will be enrolled in the study and randomized into either the intervention or control group. Based on their randomization, the study coordinator at each site will schedule either 1) a Healing Touch (HT) practitioner for the intervention group OR 2) a non-HT practitioner who will collect data for the control group, and complete demographic information from the participant's medical chart. For the intervention group, the HT practitioner will verify consent, then ask the woman to complete baseline measurements of pain and anxiety. The practitioner will administer the HT intervention. Levels of pain and anxiety will be reassessed post-intervention. For the control group: a member of the research team, will ask the woman to complete baseline measurements of pain and anxiety. The subject will then be encouraged to have 15 minutes of quiet time, with the lights dimmed. After the 15 minutes of quite time, the team member will again measure the subject's levels of pain and anxiety.

Statistical Methodology: Descriptive and inferential statistical techniques will be used to determine differences between the intervention and control groups.

1. INTRODUCTION

1.1. Specific Aims

The purpose of this clinical research project is to determine the impact of a Healing Touch intervention on pain and anxiety among patients who have undergone scheduled cesarean delivery. Additionally, the project aims to introduce HT to the obstetrical setting and examine its feasibility on an obstetrical unit.

1.2. Hypothesis

Hypothesis: Scheduled cesarean delivery patients receiving a Healing Touch (HT) intervention will report decreased levels of pain and anxiety when compared to a control group. Study Aims

Aim 1: To test the efficacy of a Healing Touch intervention on pain scores among scheduled cesarean delivery patients.

Hypothesis 1: Scheduled cesarean delivery patients will report lower pain scores after receiving a Healing Touch intervention when compared to a control group.

Aim 2: To test the efficacy of a Healing Touch intervention on anxiety scores among scheduled cesarean delivery patients.

Hypothesis 2: Scheduled cesarean delivery patients will report lower anxiety scores after receiving a Healing touch intervention when compared to a control group.

Aim 3: Explore the feasibility of providing a HT intervention on an obstetrical unit.

This will be assessed and evaluated through the course of the study as to the number of patients that are approached and decide to enroll. The research team will also be monitoring how the HT sessions can best be integrated into the daily care of the study participants.

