3. STUDY METHODS AND PROCEDURES

3.1. Study Treatment/Intervention

If the woman completes the consent form, they will be enrolled in the study and randomized into either the intervention or control group. When they are admitted to the postpartum unit after cesarean delivery, based on their randomization, the study coordinator at each site will schedule either 1) a Healing Touch (HT) practitioner for the intervention group OR 2) a non-HT practitioner who will collect data for the control group. The HT practitioners for this study will be registered nurses or HT practitioners who work in the Inova Health System and have received the minimum of Foundations of Healing Touch training. All study personnel entering patient care areas will abide by universal precautions, plus masks and face shields as required by the hospital system for infection control. For the intervention group, the HT practitioner will verify consent. Then they will ask the woman to complete baseline measurements of pain and anxiety. The practitioner will then administer the HT intervention consisting of a full body, pain management technique focusing on the surgical site, and wound sealing. HT techniques (Field Repatterning, Pain Syphon, Beak Fingers Lasering,) are techniques specific to management of pain and clearing of the energy field that have been used frequently by the nurses in their delivery of patient care. The HT intervention to be used in the proposed study has been developed by co-investigator, [name], Certified Healing Touch Practitioner and Instructor, to focus on the symptom management needs of the study participants (post-cesarean delivery) and should take no more than 15 minutes to complete. Levels of pain and anxiety will be reassessed post-intervention. Nurses providing the HT intervention will document the session and other outcomes as described below. There is a risk that the patient will not receive Healing Touch if: there is not a HT provider available or the patient is discharged prior to availability of the HT provider.

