3.4. Endpoints/Outcomes Measurements

3.4.1.Primary outcomes.

Primary outcomes will include the differences between the intervention and control groups' pre-/postintervention levels of pain (Numeric Rating Scale) and anxiety (Numeric Rating scale) (Appendix K).

Theoretical Concept and Measurement	#	Score	Reliability
	Items	Range	
Demographics			
As delineated in Data Retrieval Form	12		
Pain (Primary outcome)			
Visual Analog Scale: Measures pain intensity. Higher scores indicate higher levels of pain	1	0-10	* r =0.96 literate patients r= illiterate
Anxiety (Primary outcome)			
Hospital Anxiety Scale: Measures intensity of anxiety. Higher scores indicate higher levels of anxiety	16	0-14	Cronbach's alpha 0.73**
Healing Touch			-

* (Hawker, Mian, Kendzerska, & French, (2011). * Ferraz., Quaresma, Aquino, Atra, Tugwell, P., & Goldsmith, 1990).

**Al Aseri, Suriya, Hassan, Hasan, Sheikh, Al Tamimi, Alshathri M, Khalid N. (2015).

3.4.2.Secondary outcomes

Secondary outcomes include the relationship between HT and demographic information of the subjects. As well, the feasibility of introducing HT as a therapy for postpartum women will be assessed.

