3.5. Consent/Assent

All participants in the HT intervention group and control group will provide informed consent. Acquiring consent is a twostep process: (1) Participant returning and electronic consent via the survey platform, and then (2) the site PI/SUB-I has a conversation with the participant over the phone or face to face to review the consent. Once screened for eligibility, a member of the research team may call the potential participant using the consent phone call script (Appendix H). Whether over the phone or face to face, the study personnel will describe the study, answer any questions they may have, and if the participant is interested, email them an electronic consent form and the HIPPA authorization form if they haven't already received one. Both of these forms will be managed through an electronic platform, and securely load into the platform to be accessed by

the PI and study personnel. Participants who complete the electronic consent form will be included in the study, and randomized into either the intervention or control group. Informed consent will be confirmed again with the women prior to starting the study intervention or control session, since they may have changed their mind after delivery. One copy of the consent and HIPAA forms will be given to the participant (via email or face to face), and one will be kept in the research file for the participant, as well as being scanned into the electronic medical record.

3.6. Monitoring Subjects and Criteria for Withdrawal of Subjects from the Study.

Study participants may voluntarily withdraw from the study at any time. During the Healing Touch Therapy, the intervention would stop and a subject would be withdrawn if: The woman or her family at the bedside requested the intervention stopped, the woman reported an increase in pain and needs assistance, the woman had a self-identified change in clinical status and requested medical assistance, the woman needs to stop the session to care for the baby or get out of bed / leave the room for some reason.

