4.3. Data Storage

Information about study subjects will be kept confidential and managed according to the requirements of the Health Insurance Portability and Accountability Act of 1996 HIPAA. Privacy and confidentiality of all enrolled participants will be maintained through the use of a password protected data management spreadsheet. The spreadsheet will only be accessed on Inova computers, which are also password protected, by members of the study team who have undergone human subjects training. The spreadsheet will list all potential study subjects, including their name, medical record number and phone number, identified from the pre-surgical lists for the scheduled cesarean deliveries at each hospital site. Once a potential study subject has been screened over the phone for study eligibility and enrolled, they will receive a de-identified study "ID" which will consists of numbers and letters. The key linking the study ID to a patient's personal information will be maintained separately from collected data. Hard copies of the data collection forms will be kept in a locked metal storage file cabinet in the office of the Primary Investigator.

4.3.1.Data Management

Enrollment in the study consists of the following: A participant has signed and returned a consent form and HIPAA form in the electronic platform, AND a PI/SUB-I has confirmed consent via phone call or face to face conversation, AND the PI/SUB-I has signed the consent, AND the PI/SUB-I has screened the participant for continued eligibility AND assigned them to a study intervention. Women who complete a consent form but no other steps in the enrollment process will be reported on the spreadsheet as "healing touch provider not available", "inclusion criteria not met", "delivered before scheduled date".

Some participants may complete the consent process but cannot be scheduled for either Healing Touch or Quiet time due to availability of Healing Touch Providers. These participants will remain on the spreadsheet to maintain tracking of eligible participants, but will noted as "Healing Touch provider not available".

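### Aim 3 asks whether Healing Touch can be provided on an obstetric unit, but its only countable measure is enrolment, which gives no delivery rate under either definition of enrolment in the protocol

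*Combined protocol and SAP*

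**What the plan says.** Section 1.2 states Aim 3 as "Explore the feasibility of providing a HT intervention on an obstetrical unit". It is to be judged by "the number of patients that are approached and decide to enroll". One further sentence follows: "The research team will also be monitoring how the HT sessions can best be integrated into the daily care of the study participants". Section 3.4.2 lists feasibility among the secondary outcomes, saying that "the feasibility of introducing HT as a therapy for postpartum women will be assessed", but names no measure. Section 4.2, the analysis section, contains no feasibility analysis.

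Elsewhere the protocol foresees that HT will not always be delivered:

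- Section 3.1: "There is a risk that the patient will not receive Healing Touch if: there is not a HT provider available", or if "the patient is discharged prior to availability of the HT provider".
- Section 3.6: a session is stopped in several situations, for example when "the woman needs to stop the session to care for the baby or get out of bed".
- Section 4.3.1: some consenting women "cannot be scheduled for either Healing Touch or Quiet time due to availability of Healing Touch Providers". They stay on the tracking spreadsheet with a code for that reason.

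Enrolment is defined in two ways. The abstract (Study Methodology) and section 3.1 treat a woman as enrolled once she completes the consent form, and section 3.5 likewise includes her at that step. Section 4.3.1 asks for more: returned consent and HIPAA forms, consent confirmed in conversation and countersigned, continued eligibility, and assignment to a study intervention.

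**The concern.** Agreeing to join a trial one to two weeks before surgery is a statement about the woman's willingness. Whether a trained practitioner reaches her bedside and completes a session before discharge is a statement about the unit. Aim 3 is about the second and counts the first.

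Two wrong conclusions become possible. Feasibility could be reported as good because enrolment was good, while many women assigned to HT never had a session. Or interest could look poor when the real cause was a shortage of practitioners. A hospital deciding whether to offer HT would need to tell these apart.

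**Working it through.** **1. Inputs.** Planned recruitment is 160, 40 at each of four sites, with equal allocation (sections 2.4 and 4.1). That gives 160/2 = 80 women in the HT group and 40/2 = 20 per site. Allocation is by coin toss (section 3.3), so 80 and 20 are expected numbers, not fixed ones. The documents give no number approached, no consent rate and no delivery rate. Every such figure below is an assumption.

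**2. The plan's own figure.** None is stated for Aim 3. The sample size for the efficacy aims does reproduce: a two-sided t-test with d = 0.5, alpha 0.05 and power 0.80 needs 63.77, so 64 per group and 128 in total (power 0.801). It enters here only as background to the 160.

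**3. Enrolment counted at consent.** The count is fixed before any session takes place. Assume 80 women assigned to HT and three delivery rates:

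| HT sessions completed | Delivery rate | 95% CI (Wilson) | Enrolment count |
|---|---|---|---|
| 72/80 | 90% | 81.5% to 94.8% | same |
| 64/80 | 80% | 70.0% to 87.3% | same |
| 48/80 | 60% | 49.0% to 70.0% | same |

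The interval is centre ± half-width, with z = 1.96, where centre = (p + z²/2n)/(1 + z²/n) and half-width = z√(p(1−p)/n + z²/4n²)/(1 + z²/n). For 64/80, the centre is (0.80 + 0.0240)/1.0480 = 0.7863 and the half-width is 1.96 × √(0.0020 + 0.00015)/1.0480 = 0.0867, which gives 70.0% to 87.3%.

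**4. Enrolment counted at assignment (section 4.3.1).** Assume 400 approached, 200 consenting, and 20% of those lost before assignment because no provider was available. Then 200 × 0.20 = 40 are lost and 200 − 40 = 160 are enrolled. The reported figure is 160/400 = 40%, although 200/400 = 50% of the women agreed. The 40 women lost to staffing are merged with those who declined. Failures after assignment, such as early discharge or a stopped session, still leave no trace in the count. The 20% here and the delivery rates in step 3 are separate losses at separate stages.

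**5. Is a delivery proportion enough on its own?** Not if its denominator is only the women assigned to HT. In step 4 all 80 assigned women could complete a session (80/80), while 40/200 = 20% of consenting women never reached assignment for want of a provider. Those women belong to neither arm, so they need their own line.

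**6. Precision by site.** With 20 HT women at a site and 16 sessions completed, the centre is (0.80 + 0.0960)/1.1921 = 0.7517 and the half-width is 1.96 × √(0.0080 + 0.0024)/1.1921 = 0.1677. The rate is 80% with a 95% CI of about 58% to 92%. The pooled estimate is useful; a single site's is not precise.

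**The case against.** Aim 3 is exploratory, carries no hypothesis and is secondary. The plan is not silent on delivery either: the team will watch how sessions fit into care (section 1.2), HT sessions are documented (section 3.1), consenting women without a provider stay on the spreadsheet (section 4.3.1), and investigators meet weekly to review problems (section 7). This stands as partial mitigation, since some of the raw information will exist. But none of these provisions defines a variable or a denominator for Aim 3, and the spreadsheet entry is kept to track eligible women, not as a feasibility result.

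Three stronger readings are tempting, and the documents do not support them.

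- A reader might infer that delivery failures are simply left out of the feasibility result. Under section 4.3.1 a provider shortage before assignment can enter the count, disguised as non-enrolment. It is omitted only if enrolment is at consent.
- A reader might infer that the plan will understate acceptance, as in 40% against 50%. That follows only from section 4.3.1. Aim 3 itself speaks of the woman's decision, and the abstract and sections 3.1 and 3.5 place entry at consent. On that reading the figure would be 200/400 = 50%.
- A reader might infer that the reasons for non-delivery are already recorded. Section 4.3.1 lists three codes: no provider, inclusion criteria not met, and delivery before the scheduled date. Early discharge and stopped sessions have none. Early delivery is an exclusion criterion (section 2.8), so it is not a failure of the unit to deliver HT.

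**Conclusion.** The concern holds in this form: the stated measure for Aim 3 gives no delivery rate under either definition of enrolment. Counted at consent, it cannot vary with delivery. Counted at assignment, it can mix provider shortage with refusal. The two definitions conflict and must be reconciled in any case.

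The size is unknown, because the documents give no rates. The counts of 400, 200 and 20% and the delivery rates of 60% to 90% are illustrations, and the contrast of 40% with 50% applies only under section 4.3.1. What can be said is that about 80 HT women would support a useful pooled estimate.

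It would go too far to say that the trial can learn nothing about feasibility, given the informal monitoring and the partial tracking. Nor does the choice of measure for Aim 3 affect the analysis of pain and anxiety under Aims 1 and 2. This should be corrected, but it does not threaten the main comparison.

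**What to change.** 1. Choose one definition of enrolment and use it in the abstract and in sections 1.2, 3.1, 3.5 and 4.3.1.
2. Replace the Aim 3 measure with two proportions, each with a 95% CI:
   - (a) Acceptability: women with confirmed consent, divided by women approached, whatever the later availability of a provider.
   - (b) Delivery: women with a complete HT session before discharge, divided by all women assigned to HT.
3. Beside (b), report the number and share of consenting, still-eligible women who were never assigned or scheduled because no HT provider was available.
4. Show deliveries before the scheduled date on a separate line as ineligible, not as delivery failures.
5. Add two spreadsheet codes: discharged before the session, and session stopped.
6. Give results by site descriptively only.

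The cost is a paragraph in sections 1.2 and 4.2, two added codes and a short table. The feasibility figure may turn out less favourable than an enrolment count would have been.

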1.3. Background and Significance

During the past two decades, cesarean delivery rates have increased dramatically worldwide. Currently in the United States, nearly one third of all newborns are born by cesarean.¹ Inova Health System performed over 7 000 cesarean deliveries in 2019 (IAH 1201; IFOH 950; IFMC 4,031; ILH 872). "Women who experience cesarean births are at risk for anesthetic, surgical, and postoperative complications. They have longer hospitalizations and recoveries after childbirth compared with women who experience vaginal births".² Pain and anxiety are the most common complications after cesarean delivery. Pain is ranked highest among undesirable clinical outcomes associated with post-operative cesarean deliveries. Conventional methods of managing pain following cesarean delivery include intrathecal morphine and post-operative oral narcotic pain medications. The use of these opioids is accompanied by side effects including nausea, vomiting, pruritus, sedation, dizziness, bladder dysfunction, reduced gastrointestinal motility, and sleep pattern disturbance.³

The traditional practice of administering opioids for pain control may impair the women's abilities to remain awake and alert during the critical transition to parenting, to provide effective care for and feeding of their newborns, develop positive maternal-infant bonds, and return to optimal health. Non-pharmacological strategies for the management of postoperative pain and anxiety play an important role in routine clinical practice after cesarean delivery. Effective relief of pain and anxiety can cause comfort, enhanced quality of life, faster return to everyday life, shorter hospital stays and lower hospitalization costs. The importance of alternative pain and anxiety management strategies and decreased opioid administration cannot be overstated for this population.

One such integrative modality, Healing Touch (HT), with a foundation in holistic nursing, is a gentle therapy that uses touch to promote health and well-being by balancing the human energy system.⁴ Healing Touch (HT) is a biofield therapy in which practitioners use their hands in a heart-centered and intentional way to provide energetic balance to support physical, emotional, mental and spiritual health. It is safe for all ages and works in harmony with, is complementary to, and may be integrated with standard medical care.⁵ Healing Touch is a collection of standardized, noninvasive techniques that clear, energize, and balance the human and

¹ Martin J. A, Hamilton B.E, Osterman M.J.K, Driscoll A.K. (2019)Births: Final data for 2018. National Vital Statistics Reports; vol 68, no 13.

Hyattsville, MD: National Center for Health Statistics.

² Simmoneli, M. C., Doyle, L. T., Columbia, M. A., Wells, P. D., Benson, K. V., and Lee, C. S. (2018) Effects of Connective Tissue Massage on Pain

in Primiparous Women After Cesarean Birth. Journal of Obstetric, Gynecologic & Neonatal Nursing 47(5) ,591-601

³ Benyamin R, Trescot AM, Datta S, et al. Opioid complications and side effects. Pain Physician. 2008;11(2 Suppl):S105–S120.

⁴ Anderson, J.G., Anselme, L.C. Hart. L.K. (2017). Foundations and practice of Healing Touch. Healing Beyond Borders. Lakewood.CO.

^{5 &}quot;Healing Beyond Borders." https://www.healingbeyondborders.org/. Accessed 28 Nov. 2020.

environmental energy fields. Given the lack of harm associated with biofield therapies and the potential benefit to reduce pain and anxiety, it appears Healing Touch is an intervention worthy of exploration.

Studies have been conducted to measure the effects of Healing Touch on both acute and chronic pain. In a small study of chronic and severe pain resulting from spinal cord injury, participants who received the Healing Touch intervention reported decreased pain compared to those who received progressive muscle relaxation.⁶ There are no contraindications for using energy work to relieve pain and it can be valuable in supplementing traditional approaches or when other approaches are not successful.⁷ Studies on biofield therapies have been conducted in patients experiencing acute pain and have shown that these therapies can effectively reduce pain.⁸

Studies specifically focused on cesarean delivery pain using Reiki, another biofield energy therapy, have reported promising results. Midilli and Gunduzoglu (2016) conducted a single blinded, randomized, and double-controlled study to determine the effects of Reiki on pain and vital signs when applied to the incision area of the body after cesarean delivery.⁹ The Reiki group was observed to use fewer analgesics throughout the study and to need them after a longer time than the control groups. They concluded that after Reiki was applied for 15 minutes to the incision area after a cesarean delivery, less pain was felt and the need for analgesics was less that in the control group, but Reiki had no effect on vital signs. Another randomized-controlled clinical trial investigated the effect of Reiki on pain, anxiety, and hemodynamic metrics post cesarean delivery patients.¹⁰ The trial indicated Reiki reduced pain intensity, the value of anxiety, and breathing rate, as well as analgesic requirements post-cesarean delivery ; however, it did not affect pulse rate, and blood pressure.

Clinical effectiveness of many complementary and alternative medicine interventions has been successful in pain reduction for post-cesarean patients. Despite a growing body of research about Healing Touch as an effective intervention for postsurgical and cancer pain management, there is a paucity of literature on Healing Touch use with women during pregnancy, labor, or in the postpartum period. Since there are no adverse effects reported with the use of Healing Touch and it is a patient-centered, non- pharmacologic approach to pain management, it would seem a prudent and innovative intervention to reduce pain and anxiety. The holistic nursing concept of Healing Touch returns the nurse to the essence of nursing. Incorporating Healing Touch into nursing practice nurtures the idea of holistic nursing care and adds depth, spiritually, and individualized approach to healing. Encouraging a healing and nurturing environment for mom will enhance her ability to best care for herself and her newborn.

